### **2.3 Secondary Objectives**

1. To compare the effectiveness of the Specific Carbohydrate Diet and a Mediterranean style diet to reduce mucosal inflammation in patients with active Crohn's disease. Mucosal inflammation will be assessed by measuring the concentration of calprotectin in the feces (FCP).
2. To compare the effectiveness of the Specific Carbohydrate Diet and a Mediterranean style diet to reduce systemic inflammation in patients with active Crohn's disease. Systemic inflammation will be assessed by measuring the concentration of C reactive protein (CRP).
3. To compare the effectiveness of the Specific Carbohydrate Diet and a Mediterranean style diet to improve the following symptoms in patients with Crohn's disease: a) fatigue, b) pain, c) joint symptoms.
4. To determine the proportion of patients who continue the study diets when prepared food is no longer provided without cost and the reasons for discontinuation of the diets.

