On Day 84 (+ or – 3 days), participants will come into the clinic for a visit that will involve: collection of information about their symptoms which will be used to obtain an sCDAI score, a physical exam to obtain CDAI score, one tube of blood drawn to measure hsCRP and one for HCT, providing information about adverse events, medications, joint symptoms, providing health status information (physical, mental and social) to obtain a PROMIS score and being weighed. Participants will take a satisfaction survey about the study diet online and they will complete a Diet History Questionnaire online.. The participant will collect one stool sample during days 80-82 and ship it to [name] lab at the University of Pennsylvania. On a randomly selected day during week 12, a dietitian will contact participants by phone to ask them about what they ate on the previous day. Participants complete the study at the end of the week 12 visit.

Site Coordinators may call participants as needed to remind them of their upcoming study visits, sample collections, and online surveys.

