#### **5.7 Subject Compliance Monitoring**

Adherence to the assigned diet will be assessed using three 24-hour dietary recalls administered by trained dietitians on randomly selected days. This assessment will occur once between screening and start of study diet, once during week 6 and once during week 12. We will also have participants complete a diet history questionnaire (DHQ) at baseline and week 12. The DHQ asks about food eaten in the past 30 days. Therefore, the week 12 DHQ will be used in addition to the 24 hour dietary recall to assess adherence to the assigned diet.

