### **7.11 Other Evaluations, Measures**

24-hour dietary recalls will be used to assure adherence with the study diet. A trained dietitian will administer a phone interview to determine what participants have eaten on the randomly selected days (described above in Section 3.2.3).

An online, confidential, Diet History Questionnaire (DHQ) will be used to assure adherence with the study diet and will be completed at baseline and week 12. Patients will complete the online questionnaire at home immediately prior to or immediately following their baseline and week 12 visit. Alternatively, they may be able to complete it in the clinic if a computer with internet access is available. We will use the National Cancer Institute's web-based DHQ II questionnaire that asks about food eaten in the past 30 days. There is no patient identifying information in the DHQ. Patients log into the questionnaire with a unique code and password. The DCC will download an Excel file containing study participants' questionnaire responses from a secure https website accessible only by certain study staff at the DCC.

Study diet satisfaction surveys will be administered via an online questionnaire at the time points described in section 3.2.3. This will be a brief survey that will allow for free text comments from participants about their satisfaction and overall experience with the assigned diet.

The Patient Reported Outcome Measurement System (PROMIS) questionnaire contains several measures previously shown to correlate with disease activity and to have construct validity in CD. These include measures of fatigue, pain interference, social aspects, and sleep.

A subset of core variables found in the Multi-dimensional Health Assessment Questionnaire (MD-HAQ) will be used to assess physical function and joint pain.

We will screen for inflammatory back pain using criteria developed by Sieper et al. and assess symptom severity with the Bath AS Functional index in those who screen positive.

We will assess quality of life using a Short Quality of Life in Inflammatory Bowel Disease Questionnaire (SIBDQ) at all visits.

Patient's most recent colonoscopy results prior to the time of randomization will also be collected for those subjects with accessible records. Additionally, any colonoscopies conducted during the study or within 6 weeks of the termination visit may be requested at the opinion of the Principle Investigator.

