**Analysis of secondary outcomes (Secondary Aim 2):**

The secondary outcomes of clinical remission as assessed by the CDAI, PRO2, PRO3 reduction of hsCRP by >50% and to <5 mg/L, reduction of FCP by >50% and to a value of <250mcg/g and combined clinical remission and resolution of inflammation will be analyzed using the same methods described for the primary outcomes.

The secondary outcomes of fatigue, sleep quality, social aspects and pain interference will be measured using PROMIS short forms using the same methods as previously employed within CCFA Partners. PROMIS items are calibrated using a T score such that 50 is the mean for the general US population with a standard deviation of 10. Higher scores reflect greater level of the domain. We will compare PROMIS scores at baseline and at the end of the trial using a t-test. If there are meaningful differences in baseline scores between the treatment arms, comparison of the PROMIS measures at the end of follow-up will be adjusted for the baseline value using linear regression.

**Analysis of data from weeks 7 – 12 (Secondary Aim 3):** After week 6, participants will need to provide for the meals on their own if they choose to remain on the diet. This provides an opportunity to further assess the combined feasibility of the diets in the real world and patients' satisfaction with following the diet. Utilizing results from 24-hour dietary recalls, we will determine the proportion of patients assigned to each arm who elect to remain on the diet through week 12. We will also determine the proportion of patients who were able to discontinue steroid use by week 12 among the subgroup who were taking steroids in weeks 1-6. Finally, we will assess reasons for discontinuation of the diet among those who did not continue. Comparisons will be made using the CMH test following the principle of intention to treat. The analysis will be repeated among the subgroup of participants who achieved remission by week 6. These results will be qualitatively compared to the free text data on satisfaction and personal experience with the diets.

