Analysis of secondary outcomes (Secondary Aim 1): hsCRP data will be analyzed in the same manner as FCP data.

Analysis of secondary outcomes (Secondary Aim 2): The secondary outcomes of clinical remission as assessed by the CDAI, PRO2, PRO3 and combined clinical remission and resolution of inflammation will be analyzed using the same methods described for the primary outcomes. We will compare PROMIS scores at baseline and at the end of the trial using a t-test. If there are meaningful differences in baseline scores between the treatment arms, comparison of the PROMIS measures at the end of follow-up will be adjusted for the baseline value using linear regression.

Analysis of data from the Extension Phase (Secondary Aim 2): After week 6, participants will need to provide for the meals on their own if they choose to remain on the diet. This provides an opportunity to further assess the combined feasibility of the diets in the real world and patients' satisfaction with following the diet. Utilizing results from 24-hour dietary recalls, we will determine the proportion of patients assigned to each arm who elect to remain on the diet through week 12. We will also determine the proportion of patients who were able to discontinue steroid use by week 12 among the subgroup who were taking steroids in weeks 1-6. Finally, we will assess reasons for discontinuation of the diet among those who did not continue. Comparisons will be made using Fisher's exact test following the principle of intention to treat. The analysis will be repeated among the subgroup of participants who achieved remission by week 6. These results will be qualitatively compared to the free text data on satisfaction and personal experience with the diets.

Change from baseline stratified by treatment arm: For continuous outcome measures, such as sCDAI, PRO2, PRO3, and FCP, we will compare the week 6 and week 12 values to the baseline value using the Wilcoxon sign rank test, a nonparametric paired test. These analyses will be conducted separately for each treatment group. Imputation of missing data for this analysis will assume that the worst case scenario that the outcome measure was worse during follow-up than at baseline. (Note that approach to missing data for other analyses are described below).

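### Continuation of the diet through week 12 is to be analysed from 24-hour recalls alone, one day per participant after week 6, although protocol 5.7 commits the 30-day week-12 questionnaire to adherence as well

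*Combined protocol and SAP*

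**What the plan says.** Secondary objective 4 (protocol 2.3) has two parts, continuation and the reasons for stopping: "To determine the proportion of patients who continue the study diets when prepared food is no longer provided without cost and the reasons for discontinuation".

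**Analysis sections.** SAP 5.5.2, under the extension phase, states: "Utilizing results from 24-hour dietary recalls, we will determine the proportion of patients assigned to each arm who elect to remain on the diet", with week 12 as the end point. Protocol 8.4.2 opens the matching sentence in the same way, "Utilizing results from 24-hour dietary recalls", and names no other source. Both then assess reasons for discontinuation among those who did not continue, and repeat the analysis in participants who were in remission by week 6. The SAP compares arms with Fisher's exact test; protocol 8.4.2 uses the CMH test. Protocol 10.3 also gives the recall as the only adherence source.

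**Measurement sections.** Protocol 5.7 schedules three recalls: "This assessment will occur once between screening and start of study diet, once during week 6 and once during week 12". Protocol 3.2.3 describes the last one, which covers a single day: "On a randomly selected day during week 12, a dietitian will contact participants by phone to ask them about what they ate on the previous". On the questionnaire, 5.7 says "The DHQ asks about food eaten in the past 30 days" and that "the week 12 DHQ will be used in addition to the 24 hour dietary recall to assess adherence to the assigned diet". Protocol 7.11 agrees that the DHQ "will be used to assure adherence with the study diet and will be completed at baseline and week 12".

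In the SAP the DHQ appears only as a source of baseline diet descriptors (section 4).

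**The concern.** An analyst who follows the SAP would decide whether a participant stayed on the diet for six weeks from what that person ate on one day. Protocol 5.7 promises a second source with much longer reach, which is already collected at week 12, and neither analysis section picks it up.

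Three results depend on the classification: the continuation proportion in each arm, the comparison between arms, and the group in whom reasons for stopping are examined. The repeat analysis among week-6 remitters inherits the same classification.

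One day is a thin basis for these two diets in particular. Protocol 5.1 defines the SCD mainly by permitted and forbidden foods. It defines the MSD largely by habitual amounts (high, moderate or low intake of food groups), which a single day can hardly establish. The error may therefore differ between arms.

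**Working it through.** **1. Coverage of the self-provided period**
- Weeks 7 to 12 are 6 × 7 = 42 days (protocol 3.2.3, 5.2).
- Scheduled recalls (5.7): one before the diet, one in week 6 while food is still supplied, one in week 12. Recalls that observe weeks 7 to 12: 1, covering 1 day. Coverage = 1/42 = 2.4%.
- The week-12 DHQ looks back 30 days. Coverage = at most 30/42 = 71%. The first 42 − 30 = 12 days remain unobserved.

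**2. The sections side by side**

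| Section | Source named for adherence or continuation |
|---|---|
| Protocol 5.7 | Recall and week-12 DHQ |
| Protocol 7.11 | Recall; DHQ at baseline and week 12 |
| Protocol 8.4.2 | Recall only |
| Protocol 10.3 | Recall only |
| SAP 5.5.2 | Recall only |

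No section says which recall or DHQ pattern counts as remaining on the diet, or how the two combine.

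**3. The plan's own power figure, as a check on method**
SAP 5.2 gives 80% power for 40% v 60% remission with 97 per arm, two-sided 5%. The uncorrected chi-square formula returns 97 per arm and 80.0% power, so the figure reproduces. It concerns the primary outcome. The documents state no power for objective 4.

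**4. Illustration: equal error in both arms (all rates assumed)**
With true continuation p, sensitivity Se and specificity Sp, the observed rate is p·Se + (1 − p)(1 − Sp). Assume 50% v 70% and 97 per arm.

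| Se = Sp | Observed rates | Gap | Chi-square power | Fisher's exact power |
|---|---|---|---|---|
| 100% | 50% v 70% | 20 points | 82% | 77% |
| 90% | 50% v 66% | 16 points | 62% | 56% |
| 80% | 50% v 62% | 12 points | 39% | 34% |

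For example, at 90%: 0.70 × 0.90 + 0.30 × 0.10 = 0.66. Fisher's exact test is the one SAP 5.5.2 names for this comparison.

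**5. Illustration: error that differs by diet (all rates assumed)**
- SCD Se/Sp 0.80/0.90 and MSD 0.90/0.70, true rates 50% v 70%. SCD: 0.50 × 0.80 + 0.50 × 0.10 = 45%. MSD: 0.70 × 0.90 + 0.30 × 0.30 = 72%. The gap widens from 20 to 27 points.
- Same error rates, true rate 60% in both arms. SCD: 0.60 × 0.80 + 0.40 × 0.10 = 52%. MSD: 0.60 × 0.90 + 0.40 × 0.30 = 66%. A false gap of 14 points appears.
- Error rates swapped between arms, true rates 50% v 70%. SCD: 0.50 × 0.90 + 0.50 × 0.30 = 60%. MSD: 0.70 × 0.80 + 0.30 × 0.10 = 59%. The true gap all but disappears.

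**The case against.** The strongest reply is that protocol 5.7 already commits the week-12 DHQ to adherence and 7.11 supports it, so the plan as a whole does not rely on one day. That is right as far as it goes. A reader might infer that all of secondary objective 4 rests on one day's eating, and the documents do not support that. Two sections assign the DHQ to adherence, and the reasons for discontinuation are not themselves taken from the recall. What stands is narrower: the sections that govern the analysis omit the DHQ, and the only source they name for identifying non-continuers is the recall.

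A reader might also infer that one lapse makes an adherent participant a discontinuer. No section sets that threshold, or any other. The missing rule is part of the defect.

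Some stopping would be known without the recall. Protocol 6.5 keeps participants who abandon the diet for reasons other than worsening disease in follow-up to the next visit. Protocol 6.3 and 6.5 withdraw those whose Crohn's treatment changes. Satisfaction surveys with free text run at weeks 9 and 12. This reduces the practical risk, but neither analysis section says that any of it feeds the classification.

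Finally, the DHQ is also self-report and misses at least 12 of the 42 days. It improves coverage but is not a reference standard.

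**Conclusion.** The concern holds as a conflict between sections with a consequence for analysis. Protocol 8.4.2 and SAP 5.5.2 (and 10.3) name the recall alone, which observes one day of 42. Protocol 5.7 requires the DHQ as well, which observes up to 30 of 42. None of them defines continuation.

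The coverage figures follow from the documents. The size of any bias does not, because sensitivity, specificity and true continuation are all assumed above. It would be tempting to say that misclassification pulls the arms together. That is so only if error is equal in both arms; where it differs by diet, the bias can go either way or create a difference where none exists. It would also be tempting to report a loss of power as a finding. The plan claims no power for this objective, and protocol section 2 calls the secondary aims exploratory, so the power figures are illustrative only.

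The primary analysis is unaffected. This is a minor point, worth correcting because the remedy uses data the trial already collects.

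**What to change.** In protocol 8.4.2 and SAP 5.5.2, classify continuation from the week-12 DHQ together with the week-12 recall, and align 10.3 with 5.7. Before analysis, specify:

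- the diet-specific DHQ and recall pattern that counts as remaining on the diet, for each arm;
- how a participant is classed when the two sources disagree;
- that a participant with neither source counts as not continuing, in line with the plan's rejection of complete-case analysis;
- a sensitivity analysis using the recall alone.

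While the text is open, settle whether Fisher's exact test or the CMH test applies to this comparison, since the two sections differ.

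The cost is SAP wording and modest scoring work, because the documents contain no adherence score for either instrument. No new data are needed. The remaining limits are that the DHQ is self-report and covers at most 30 of the 42 days.

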14. BMI <16
15. BMI ≥40
16. Celiac disease
17. Documented C difficile colitis within four weeks of screening
18. Diabetes Mellitus requiring medication
19. Albumin<2.0mg/dl, within 4 weeks of screening (if tested as part of routine clinical care)
20. Known allergy to tree nuts or peanuts
21. Other conditions that would be a contraindication to any of the study diets or preclude the participant from completing the study.
22. Currently participating in another clinical trial of a drug to treat IBD or a dietary therapy for any indication.

\*Patients may continue these medications at stable dose for the first six weeks and budesonide may be used at any dose. After the 6th week in the study, patients may taper their steroid dose. The study will provide a recommended taper schedule.

\*\*Loading/induction doses of biologic type medication will be considered a stable doses.

\*\*\*Exception for treatment failures: if a subject is determined to fail on any of the following standard lines of treatment at the treating investigator's discretion, subjects may screen for study intervention based upon the following wash out periods: 4 weeks for thiopurine and methotrexate and 8 weeks for natalizumab, vedolizumab, anti-TNF, or ustekinumab.

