## **6.5 Subject Withdrawal**

Participants may withdraw from the study at any time.

Participants may be withdrawn at the discretion of the investigator prior to randomization for the following reasons:

- Failure to provide the baseline stool sample
- Failure to complete at least 5 of the 7 baseline sCDAI surveys

Participants will be withdrawn from the study if they experience worsening symptoms requiring a change in their Crohn's disease treatment, the initiation of an antibiotic for gastrointestinal symptoms, and/or an increase of greater than 10mg/day of prednisone or equivalent for a non-gastrointestinal condition\*.

*\*Please see section 6.2.2 for equivalency chart*

Participants who have been randomized to one of the two diets and withdraw early from the study should complete an end of study visit and provide a stool sample at the time of withdrawal as described in section 6.2.5.

If the participant wishes to discontinue the study diet early for reasons not related to worsening Crohn's Disease (e.g., they don't like the diet), they will be asked to remain in follow-up and complete the next in-person visit at the target date of that visit (either week 6 or week 12). This will be the end of study visit.

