#### **8.5 Subject Population(s) for Analysis**

As a comparative effectiveness study, the primary efficacy and safety analysis will use the principle of intention to treat such that all randomized patients will be included in the group that they were randomized to, regardless of the level of adherence with the assigned diet.

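### The extension-phase comparisons are repeated between arms among week-6 remitters and labelled intention to treat; if the diets differ in remission, this repeat can be biased against the diet with more remitters.

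*Combined protocol and SAP*

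**What the plan says.** SAP 5.5.2 (Extension Phase) and protocol 8.4.2 (weeks 7 to 12) plan the same sequence. The share of each assigned arm still on its diet at week 12 is determined from dietary recalls. Steroid discontinuation by week 12 is assessed "among the subgroup who were taking steroids in weeks 1-6", and reasons for stopping the diet are collected. Then: "The analysis will be repeated among the subgroup of participants who achieved remission by week 6".

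The two places name different tests. The SAP has "Comparisons will be made using Fisher's exact test following the principle of intention to treat"; the protocol has "Comparisons will be made using the CMH test following the principle of intention to treat". Protocol 8.5 gives the meaning of that principle: "all randomized patients will be included in the group that they were randomized to".

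Three other passages bear on the point:
- Symptomatic remission at week 6 is the primary endpoint (protocol 3.4.1.1), and SAP 5.2 sizes the trial on 40% with the Mediterranean style diet (MSD) and 60% with the Specific Carbohydrate Diet (SCD).
- On corticosteroids, the note to protocol 4.2 says "Patients may continue these medications at stable dose for the first six weeks", and protocol 6.5 says "Participants will be withdrawn from the study if they experience worsening symptoms requiring a change in their Crohn's disease treatment".
- Protocol section 2 describes the secondary aims as exploratory. The hypothesis-generating caveat in SAP 5.5.2 is attached to the effect-heterogeneity subgroups, not to these analyses.

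**The concern.** Randomisation makes the two arms comparable as wholes. It does not make the remitters in one arm comparable with those in the other when the diets produce different numbers of remitters. If SCD brings into remission patients who would not have remitted on MSD, the SCD remitters include an extra group that the MSD remitters lack. If those patients also have a poorer outlook for week 12, the SCD remitters look worse even when diet has no effect on the week-12 outcome.

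Whether patients stay on the diet once food is no longer supplied is a stated objective (protocol 2.3, item 4). A p-value under an intention-to-treat label would invite readers to treat the remitter contrast as a randomised one. The bias can also hide a real advantage of the diet with more remitters.

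**Working it through.** **1. The plan's own figure.** Inputs from SAP 5.2: 40% v 60%, 97 per arm, two-sided 5%, chi-square test. The two-proportion formula without continuity correction gives n = 97 per arm and power 0.800, so the stated figure reproduces. The plan gives no figure for the extension-phase subgroups.

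**2. Size of the remitter groups.** At the design rates, 97 × 0.40 ≈ 39 MSD and 97 × 0.60 ≈ 58 SCD patients enter the repeat.

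**3. Simulation with no diet effect on the week-12 outcome.** Assumed, because the documents give no values: a week-12 outcome rate of 50% overall, and a correlation rho between the latent tendencies to remit and to reach the week-12 outcome. There were 6,000 simulated trials per setting, 97 per arm, Fisher p < 0.05, among remitters only.

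| Remission MSD v SCD | rho | SCD minus MSD, points | Rejection |
|---|---|---|---|
| 40% v 40% | 0 to 0.7 | about 0 | 3.3-3.5% |
| 40% v 60% | 0 | about 0 | 3.9% |
| 40% v 60% | 0.3 | -4.0 | 5.4% |
| 40% v 60% | 0.5 | -6.6 (70.0% v 63.4%) | 8.7% |
| 40% v 60% | 0.7 | -9.9 | 15.4% |
| 20% v 40% | 0.3 | -5.2 | 4.9% |
| 20% v 40% | 0.5 | -8.0 | 6.6% |
| 20% v 40% | 0.7 | -9.7 | 8.7% |

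The same outcome compared over all randomised patients (97 v 97) is rejected in 3.3-4.0% of trials in every setting. Fisher's test is conservative here, so about 4%, not 5%, is the benchmark for no bias.

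**4. Worked illustration with assumed continuation rates.** Suppose 40% remit on either diet and 80% of them continue. A further 20% remit only on SCD, and 50% of them continue. MSD remitters continue at 80%; SCD remitters at (40 × 0.8 + 20 × 0.5)/60 = 70%. Exact enumeration of Fisher's test at 39 v 58 gives 15% rejection (a normal approximation gives 19%). With extreme rates of 90% and 30%, the figures are 90% v (40 × 0.9 + 20 × 0.3)/60 = 70%, and 63% rejection (66% by normal approximation).

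**5. Steroid subgroup.** Assume b baseline users per arm, half of whom discontinue in both arms, and count anyone who starts steroids after randomisation as not discontinued. The proportion in an arm with m starters is 0.5b/(b + m).
- No starters, or equal starters in both arms: difference 0.
- 5 MSD and 2 SCD starters: b = 10 gives 33.3% v 41.7% (+8.3 points); b = 30 gives 42.9% v 46.9% (+4.0).
- 10 MSD and 3 SCD starters: +13.5 points at b = 10 and +8.0 at b = 30.

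Defining the group by baseline use removes the starters, and the difference returns to 0.

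**The case against.** Five points can be made for the plan.

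- **The aims are exploratory, and continuation is first compared on everyone assigned.** This stands and limits the severity. A general exploratory label still does not tell a reader that this one contrast has lost the protection of randomisation.
- **Bias needs two conditions together.** This also stands. A reader might infer that the remitter repeat shows a false difference in any event; with 40% v 40% remission, or with rho at 0, it does not. The first condition, however, is the trial's own hypothesis, and the second is plausible.
- **Intention to treat is also explained, in protocol 8.4.2 and SAP 5.5, as classification by assigned arm whatever was eaten.** The repeat respects that part. It does not meet the all-randomised definition in protocol 8.5.
- **The steroid subgroup is mostly a baseline group.** A reader might infer that it is compromised to the same degree as the remitter subgroup. The documents do not support that. Users at entry may stay on a stable dose, patients whose worsening requires a treatment change are withdrawn, and nothing says withdrawn starters are counted in this denominator. If one diet led to more steroid starts, that would itself be a real diet effect, although it would blur what the proportion measures. What remains is that the literal wording admits starters.
- **A composite of remission and continuation is not a substitute.** In the first illustration it would be 32% v 42% (0.40 × 0.8 = 0.32; 0.32 + 0.20 × 0.5 = 0.42). That gap comes entirely from week-6 remission, so the composite largely re-tests the primary endpoint.

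**Conclusion.** The point holds for the remitter repeat. Its subgroup is defined by the primary outcome, and the intention-to-treat label does not fit it. If the diets differ in week-6 remission and prognosis carries through to week 12, the contrast is biased, typically against the diet with more remitters.

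At 40% v 60% remission the spurious deficit is about 0 to 10 points, with roughly 4% to 15% rejection. This rests on the assumed 50% outcome rate and rho of 0 to 0.7. A reader might infer from the 90%/30% illustration that a false positive is more likely than not. That 63% depends on extreme continuation rates with no source in the documents and is at most the far end of a range.

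The steroid definition is a minor matter of wording. Severity overall is low to moderate.

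**What to change.** 1. In SAP 5.5.2 and protocol 8.4.2, keep the all-randomised comparison of diet continuation as the between-arm test.
2. Report continuation and steroid figures among week-6 remitters by arm as descriptive, without a between-arm test and without the intention-to-treat label.
3. Optionally, add the proportion of all randomised patients who are in remission at week 6 and on the assigned diet at week 12, noting that it also reflects the week-6 remission difference.
4. Define the steroid-discontinuation subgroup as participants on corticosteroids at baseline. SAP section 4 already lists this variable.
5. Name one test in both places. At present the SAP has Fisher's exact and the protocol has CMH.

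The cost is wording in two sections, with no new data. The downside is that the remitter repeat loses its p-value.
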